1.0 Objectives / Specific Aims

The overall aim of this proposed effort is to test transcutaneous auricular neurostimulation (tAN) as a therapeutic for opioid withdrawal and neonatal abstinence syndrome (NAS).

We hypothesize that tAN delivered for up to 60 minutes during peak withdrawal (1h before next morphine dose) will be safe, well tolerated and will decrease Finnegan withdrawal scores and shorten the length of morphine treatment compared with historical data.

Aim 1: Determine the safety and feasibility of auricular neurostimulation therapy in neonates with opioid withdrawal or NAS.

We hypothesize that auricular neurostimulation is safe and tolerable in both a single session, and 12-day treatment course. Furthermore, we believe target engagement can be validated by measuring stimulation-induced reductions in heart rate. Milestone: No adverse events of bradycardia (HR < 80 bpm), worsening of swallowing or feeding, skin irritation, or elevation of Neonatal Infant Pain Scores.

Aim 2: Demonstrate that auricular neurostimulation therapy in opioid withdrawing or NAS neonates reduces the Finnegan and/or WAT-1 scores from pre- to post-stimulation. We have used ear electrodes for taVNS in a similar stuy (#67997). However, in this prospective, open-label study we will use a novel, non-significant risk auricular neurostimulation device and ear electrodes to study 20 opioid withdrawing or NAS neonates at the Medical University of South Carolina. We aim to show a clinically-meaningful reduction in Finnegan scores, the routine assessment that includes 21 signs of withdrawal (Finnegan 1992). Alternatively, in infants who receive both opioids and benzodiazepine analgesics, we aim to show a clinically-meaningful reduction in Withdrawal Assessment Tool (WAT-1) scores, which is a validated, 11 item/12 point scale used to monitor opioid withdrawal in pediatric patients (Franck 2008). In the study, we will deliver up to 60 minutes of tAN 1 hour prior to each morphine administration, up to 4 times per day for up to 12 days. If morphine is weaned off at or before 10 days, a weaning phase for tAN will begin on the following day for 2 days: tAN Weaning Day 1: deliver tAN twice tAN Weaning Day 2: deliver tAN once We will assess each patient with standard Finnegan scores and/or WAT-1 before and after stimulation, and monitor use of morphine throughout the study. We expect a 25% reduction in Finnegan/WAT scores from before to after sessions of auricular neurostimulation.

Drs. [name] and [name] have an IRB-approved protocol (#67997) for studying the use of transcutaneous auricular vagus nerve stimulation (taVNS) for improving oromotor function in newborns. In our taVNS protocol we use an ear clip electrode to devlier the stimuatlion, but this electrode has the disadvantage of becoming displaced with head turning, burping etc. Therefore, we propose to use Spark Biomedical company's non-invasive, auricular neurostimulation device in this study to treat opioid withdrawal symptoms of babies with NAS. This device will be placed in the ear (similar to a hearing aid) and will target trigeminal and vagal nerve branches. Stimulation will be delivered transcutaneously via a hydrogel interface similar to the standard EMG and EKG leads we currently use in #67997. This device has proven to be safe across many indications with the only side effect being skin irritation. Spark Biomedical is curenlty working on FDA clearance for adult opioid withdrawal based on predicate devices (K173861, DEN170018). This product will be regulated as a Class II medical device by the FDA.

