4.0 Study Endpoints

Safety Outcomes: 1) Skin irritation, assessed by staff daily. 2) NIPS pain scores recorded during treatment.

Efficacy Outcomes: 1) Finnegan scores before and after tAN will be recorded at each session or WAT-1 scores will be recorded with hands on care . 2) Duration of morphine weaning. 3) Length of stay We will also collect data on developmental outcomes from a short motor test in the nursery and from routine clinic visits to the NICU high-risk follow-up clinic up to 24months.

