5.0 Inclusion and Exclusion Criteria/ Study Population

Inclusion criteria: Neonates or infants with opioid withdrawal or NAS who have withdrawal scores requiring morphine replacement therapy. They must be clinically stable, on minimal respiratory support (Continuous positive airway pressure (CPAP), nasal cannula, or room air), >33 weeks gestational age at enrollment, and currently receiving replacement therapy for opioid dependence.

Exclusion criteria:

- 1) Unstable infants or those requiring significant respiratory support.
- 2) Repeated episodes of autonomic instability (apnea or bradycardia) which are not self-resolving *
- 3) Infants <33weeks gestation at enrollment.
- 4) Major unrepaired congenital anomalies
- 5) Cardiomyopathy

*Preterm infants commonly have short periods of shallow or absent breathing or lower heart rate termed apnea and bradycardia, respectively, and most are being treated for these physiologic manifestations of prematurity with caffeine, an effective central stimulant. Infants are on cardiorespiratory monitors through the nursery stay with recording devices to capture events and play them back. However, nearly all of these events are self resolving, meaning the infant resolves the breathing pause or bradycardia on their own. Infants who require repeated episodes of stimulation to come out of these events are defined as *unstable*. Similarly, infants on significant respiratory support are not stable, and will not be eligible.

Stable neonates who are dependent on opioids, such as after ECMO, severe illness or brain injury, will be included in this study, as these neonates represent a population in which tAN could minimize withdrawal while not adding to burden of pharmacotherapies. Congenital syndromes may be included if the infants do not have major, unrepaired anomalies.

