Participants will receive tAN stimulation to their left ear via electrodes attached to the ear. The stimulation intensity we will use for tAN will be ~0.1mA less than PT or each infant. We will recalibrate the PT daily, and then deliver that current intensity for each session that day administered every 3h, starting 1h before the morphine dose. The current will be on for 5 minutes, off for 10 seconds, for up to 60 minutes total each session, up to 4 times per day, for up to 12 days or until morphine is weaned off. If morphine is weaned off at or before 10 days, a weaning phase for tAN will begin on the following day for 2 days. tAN Weaning Day 1: deliver tAN twice. tAN Weaning Day 2: deliver tAN once.

The nurses will score the NAS using the Finnegan scale before and after the treatment. The Withdrawal Assessment Tool (WAT-1) will also be used to assess infant withdrawal symptoms before and after treatment in infants receiving benzodiazepines and opioids (Franck 2008, 2013). The WAT-1 is an 11 item/12 point scale to monitor withdrawal and is routinely performed by nurses 3 times per 12 hour shift with hands on care.

Prior to beginning the study, Drs. [name] and [name] will perform an in-depth in service with the charge nurses of the neonatal nurseries, a limited pool of 10 nurses. They will also in-service the neonatal nurses at their staff meetings to introduce them to the study, the rationale, the protocol and the equipment. Most nurses are familiar with ear electrode stimulation from the taVNS-paired feeding study conducted over the past 18 months.

A short developmental test, the STEP, will be performed while the infant is stil in the nursery and at the first neonatal high-risk developmental clinic (outpatient) follow-up visit.

Safety Monitoring

Prior to determination of the daily sensory threshold of the infant by the study coordinator or research assistant, an initial pain level will be recorded using the NIPS. The nurse or other staff may decrease the current intensity or stop stimulation entirely if the infant shows signs of distress or an increase in NIPS score >3 above baseline. As opioid withdrawing infants frequently have higher NIPS, we will only halt or adjust stimulation if the NIPS is 3 greater than their baseline. The nursing staff routinely measure and record the NIPS throughout the day. We will monitor the relationship of increased NIPS scores to the up to 60 minute stimulation period daily.

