Switching from left to right ear in case of left ear difficulties

Skin redness at the site of tAN attachment to the ear is possible after treatment, but is expected to be transient. In order to prevent injury to the skin in contact with the device, each day the left ear will be first examined for redness or other medical device placement prior to attaching the tAN earpiece. If there is skin redness or any emergent medical needs at the site of attachment to the ear prior to each day's treatment, we will switch the site of stimulation to the right ear until redness or emergent medical needs on left ear are resolved.

Estimated Difficulties, Limitations and Time Frames

Estimated Difficulties: Many of the initial difficulties surrounding taVNS in humans, such as feasibility, were accomplished in the taVNS-feeding pilot trial at MUSC by [name] and [name] that were approved by IRB 1. Electrode placement: The ear electrode is easy to fit to the infant's ear and much less likely to become dislodged due to head movement than the ear electrodes used in our taVNS infant feeding study. However, we will make sure the staff feel comfortable placing the electrodes and be on call to assist with electrode placement as needed for night shift nurses. The program will be either on or off switch for nurses to activate, but will have ability to decrease stimulation current as needed.

Limitations: Finnegan scores may not show a difference acutely with tAN treatment, but may lead to faster morphine weaning. However, this is not a randomized study, and we will not be able to determine if this is significant, as it will have to be compared with historical control data already collected and analyzed in Pro # 63667. Nevertheless, we will show feasibility and safety, and gather data for a larger randomized study.

Estimated Time Frames. We plan on completing enrollment in this study over a 6-12 month period.

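### The morphine outcome has two names and no common starting point, and infants enrol already on treatment, so the size, and possibly the sign, of the historical comparison depends on where counting starts

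*Protocol*

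**What the plan says.** The overall hypothesis in Protocol Section 1.0 is that tAN will lower withdrawal scores and "shorten the length of morphine treatment compared with historical data". The second efficacy outcome in Section 4.0 is "Duration of morphine weaning". No start or stop event is attached to either name, and nothing says that they are the same quantity.

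Section 5.0 requires infants to be "currently receiving replacement therapy for opioid dependence", with no upper limit on time since the first dose. It also widens the population beyond NAS: "Stable neonates who are dependent on opioids, such as after ECMO, severe illness or brain injury, will be included in this study".

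Section 10.0 has stimulation continue "for up to 12 days or until morphine is weaned off". Under Limitations it says of faster weaning that "it will have to be compared with historical control data already collected and analyzed in Pro # 63667", and concedes that "this is not a randomized study, and we will not be able to determine if this is significant". The only analysis described, in Section 12.0, is a paired test of Finnegan scores. Planned enrolment is 20, as a convenience sample without a power calculation.

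**The concern.** The two names can describe different intervals. Treatment can include days before any dose reduction, and weaning need not. More important is the eligibility rule, under which every trial infant enters some time after morphine began. That leaves two plain ways to count, and each can go wrong against unselected historical infants:

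- **From enrolment.** The days already used are dropped for trial infants but kept for historical infants. tAN looks too good.
- **From first dose.** Infants who came off morphine before they could enrol are missing from the trial group but present in the historical group. tAN looks too poor.

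The estimate is a stated hypothesis and a listed efficacy outcome, and Section 10.0 says that the study will supply data for a larger randomised trial. A starting-point artefact could be carried into that planning as if it were a device effect.

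**Working it through.** **No figure to reproduce.** The protocol gives no mean, spread, target difference or power for morphine duration. The nearest figures, 16.9 and 25 days in Section 2.0, are lengths of stay. Every input below is therefore an assumption.

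**Model with no device effect.** Let T be the full morphine duration, gamma distributed with mean m and coefficient of variation CV. Let E be the treatment day at enrolment, uniform on days 1 to 7 or 1 to 14. An infant can enrol only if T > E. Historical infants contribute all of T, so their mean is m.

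- Bias when trial infants are counted from enrolment: mean(T − E | T > E) − m
- Bias when they are counted from first dose: mean(T | T > E) − m

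Results in days, by simulation (negative means that tAN looks shorter):

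| Entry days | m | CV | From enrolment | From first dose |
|---|---|---|---|---|
| 1–7 | 12 | 0.4 | −3.7 | +0.2 |
| 1–7 | 12 | 0.6 | −2.8 | +1.0 |
| 1–7 | 17 | 0.4 | −3.9 | +0.1 |
| 1–7 | 17 | 0.6 | −3.2 | +0.7 |
| 1–7 | 25 | 0.4 | −4.0 | 0.0 |
| 1–7 | 25 | 0.6 | −3.5 | +0.5 |
| 1–14 | 12 | 0.4 | −5.1 | +1.3 |
| 1–14 | 12 | 0.6 | −3.7 | +2.6 |
| 1–14 | 17 | 0.4 | −6.2 | +0.9 |
| 1–14 | 17 | 0.6 | −4.5 | +2.3 |
| 1–14 | 25 | 0.4 | −7.0 | +0.4 |
| 1–14 | 25 | 0.6 | −5.4 | +1.8 |

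**How one setting arises.** Fix entry at day 5 with m = 17 and CV 0.6. About 93% of durations exceed 5 days, and their mean is 18.0. From first dose the apparent difference is 18.0 − 17 = +1.0 day. From enrolment it is (18.0 − 5) − 17 = −4.0 days. The two counts differ by exactly the 5-day lag.

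**Does the sign change when there is a true effect?** This used fixed lags of 1, 3, 5 or 7 days, means of 12, 17 or 25 days and CV 0.4, 0.6 or 0.8, which makes 36 settings. A true effect shortened only the time after enrolment.

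- True 10% shortening: the first-dose count shows a lengthening in 11 of 36 settings.
- True 25% shortening: it does so in 4 of 36.
- Lag of 1 day: the sign never flips with either effect.
- Count from enrolment: always negative, and too large.

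**Scale.** Against a fixed historical mean, the difference detectable with 80% power and two-sided 5% is (1.96 + 0.84) × SD / √20. For m = 12 and CV 0.4 (SD 4.8) this is 2.80 × 4.8 / 4.47 = 3.0 days. For m = 25 and CV 0.8 (SD 20) it is 12.5 days. The enrolment-count bias can exceed the lower end of that range.

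**The case against.** The strongest reply is that this is detail for an analysis plan that is not shown. The protocol nowhere commits to counting trial infants from enrolment and historical infants from first dose. The two names may be loose synonyms. The unseen historical protocol may have selected and counted its infants in a matching way, in which case the bias shrinks or disappears. The comparison is in neither numbered aim, and Section 10.0 disclaims significance for it.

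Much of this limits the point. A reader might infer that the sign of the result is bound to turn on the starting point, or that a useless device could appear to lengthen treatment by several days. The documents support neither reading. They give no morphine durations, spread or enrolment lag, and with a short lag or a larger true effect the sign does not change. With first-week entry and CV up to 0.6, the first-dose bias is at most 1.0 day. That is below one standard error of a 20-infant mean in every such setting (SD / √20 is 1.1 to 3.4 days). Nor is it shown that two distinct endpoints are intended, since the wording is ambiguous.

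What stands is that the hypothesis, the outcome name and the eligibility rule are protocol content, and together they leave the quantity undefined. The disclaimer concerns significance and gives lack of randomisation as its reason. Leaving out a p-value does not remove bias from the estimate.

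**Conclusion.** The concern holds in this form: the morphine outcome is named inconsistently and has no time zero, and infants join after treatment has begun, so the size of the historical comparison depends on where counting starts and its sign may too. With no true effect, the gap between the two counts equals the average lag at enrolment. That is about 4 days for first-week entry and 6 to 7 days for entry over two weeks, under the assumed gamma durations and uniform entry. Most of it falls on the enrolment count, which favours tAN; the first-dose error is smaller and runs against it. The true lag and the historical counting rule are unknown. For a safety and feasibility study this should be corrected, but it does not undermine the safety aim or the before-and-after comparison of scores.

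**What to change.** 1. Use one endpoint in Sections 1.0 and 4.0: days from the first to the last dose of morphine given as withdrawal replacement therapy. For iatrogenic dependence, count from the start of replacement therapy and not from sedation. Apply the same definition to the historical infants.
2. Record the replacement-therapy day at enrolment for every trial infant.
3. Compare by delayed entry: each trial infant joins the risk set on that day and is compared only with historical infants still on morphine on the same treatment day. In the model above this makes the no-effect difference zero by construction. Report NAS and iatrogenic infants separately.
4. Report the estimate with a confidence interval as descriptive, and word the Section 1.0 hypothesis to match the Section 10.0 limitation.

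**Cost.** Items 1, 2 and 4 need wording and one date from the chart. Item 3 loses some precision and needs infant-level durations from Pro # 63667. Section 10.0 says these data are already collected, but whether they are available in that form is not stated. If they are not, the protocol should say that the comparison is biased and draw no conclusion on shortening. Delayed entry aligns the clock only; it does not remove differences in case mix or calendar time between trial and historical infants.

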6.0 Number of Subjects

Total Planned Enrollment: 20

Up to twenty neonates will be enrolled in this prospective, open-label safety and feasibility trial. The experimental paradigm consists of up to 60 minutes of tAN at the peak withdrawal time 1 hour before usual morphine dose every 3h, before feeding, up to 4 times per day, and up to 12 days or until morphine is weaned off. If morphine is weaned off at or before 10 days, a weaning phase for tAN will begin on the following day for 2 days:

- tAN Weaning Day 1: deliver tAN twice
- tAN Weaning Day 2: deliver tAN once

All consented participants will receive the active stimulation condition.

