12.0 Data Management

Limited demographic and personal health history data will be collected for the study. All screening data will be identified only by study number except for the consent form and a master enrollment file, which will be kept in a binder a the locked office, and password protected, respectively, per the requirements of the IRB.

All infants will be withdrawing from opioids, and will have had urine or meconium drug screens per clinical protocol. Also all fetal drug exposures will be a matter of clinical record, and not obtained for this study. We will not be doing any drug screening for this study. Study records will be kept confidential. However, as we will only have substance use information which is included in the clinical record and already known/reported to social services, we will not obtain a certificate of confidentiality.

Power Calculation: N/A. This is a convenience sample. We estimate we can enroll up to 20 patients within 12 months.

Statstical Analysis: tAN Finnegan scores obtained before and after will be compared within subjects by paired test.

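### Zero events in at most 20 infants cannot show safety: even a clean result leaves per-infant rates up to 13.9% not excluded

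*Protocol*

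**What the plan says.** Aim 1 in section 1.0 is to determine safety and feasibility. Its hypothesis is: "We hypothesize that auricular neurostimulation is safe and tolerable in both a single session, and 12-day treatment course". The only criterion attached to the safety part is: "Milestone: No adverse events of bradycardia (HR < 80 bpm), worsening of swallowing or feeding, skin irritation, or elevation of Neonatal Infant Pain Scores".

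The Limitations paragraph of section 10.0 concedes that the weaning result cannot be judged without randomisation, and then continues: "Nevertheless, we will show feasibility and safety, and gather data for a larger randomized study".

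On size, section 6.0 gives "Total Planned Enrollment: 20" and adds: "Up to twenty neonates will be enrolled in this prospective, open-label safety and feasibility trial". Section 12.0 gives the basis for that number: "Power Calculation: N/A. This is a convenience sample. We estimate we can enroll up to 20 patients within 12 months". The one analysis it states concerns efficacy: "tAN Finnegan scores obtained before and after will be compared within subjects by paired test".

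The protocol names no event rate that safety data should exclude and no minimum number of treated infants. Section 4.0 lists only two of the four milestone event types among its outcomes: "Safety Outcomes: 1) Skin irritation, assessed by staff daily. 2) NIPS pain scores recorded during treatment".

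**The concern.** A count of zero is an observation whose meaning depends on how many infants stand behind it. The milestone gives no such number and no rate to be ruled out, while section 10.0 states in advance that safety will be shown. A reader of the final report could take a clean result as settling the matter, when 20 infants can exclude only fairly high rates.

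The safety statement is also less guarded than the efficacy statement beside it. The Limitations paragraph admits what the design cannot say about weaning but sets no matching limit on safety, although the same small, uncontrolled sample supports both.

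At stake is the claim carried into the larger randomised study that section 10.0 says this trial prepares. If that study starts from safety having been shown, its own monitoring may be planned on a firmer footing than the data give.

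**Working it through.** **Inputs from the protocol.** Zero events allowed, of four types (1.0, Aim 1). Planned enrolment 20, described as up to 20 (6.0). Convenience sample, no power calculation (12.0). There is no stated calculation to reproduce.

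**Assumptions.** The protocol gives no per-infant event rates and no confidence level. I use 95%, treat infants as independent, and take illustrative true rates of 5% and 10%.

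**Step 1: what zero events excludes.** After 0 of n, the exact (Clopper-Pearson) upper bound is 1 − 0.05^(1/n) one-sided and 1 − 0.025^(1/n) for the two-sided limit. At n = 20 these are 1 − 0.05^(1/20) = 0.139 and 1 − 0.025^(1/20) = 0.168.

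| Infants treated, no event | One-sided 95% bound | Two-sided 95% limit |
|---|---|---|
| 20 | 13.9% | 16.8% |
| 15 | 18.1% | 21.8% |
| 10 | 25.9% | 30.9% |

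To bring the one-sided bound below U with no events needs ln(0.05)/ln(1 − U) infants, rounded up: 29 for U = 10% and 59 for U = 5%. Both exceed the planned maximum, so even the best possible result here cannot exclude a rate of 1 infant in 10.

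**Step 2: chance of a clean result for one event type.** P(no event) = (1 − p)^n.

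- p = 5%, n = 20: 0.95^20 = 0.36
- p = 10%, n = 20: 0.90^20 = 0.12

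An event type that truly affects 1 infant in 20 would therefore go unseen about a third of the time with full enrolment. The rate at which 20 infants have an 80% chance of showing at least one event is 1 − 0.2^(1/20) = 7.7%.

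**Step 3: the milestone as written.** It requires zero of all four types at once. If each has an independent per-infant rate p, P(milestone met) = (1 − p)^(4n). With p = 5% and n = 20 this is 0.95^80 = 0.0165, about 1.7%. Independence between types is a further assumption, and positive correlation would raise the figure.

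**Step 4: reading the steps together.** For any single event type, zero is weak evidence of a low rate. For the four together, zero is a demanding target that a tolerable device would often miss. Section 10.0 itself says that redness at the attachment site is possible, and section 5.0 notes that preterm infants commonly have short episodes of lower heart rate. One transient event would fail the milestone; no events would pass it. Neither outcome describes the rates.

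**The case against.** The strongest reply is that this is a small pilot and that interval methods for event proportions can be left to a statistical analysis plan, which is not shown. The protocol also hedges: it calls its criterion a milestone, says in section 15.0 that there may be unknown risks, and defers to a larger study. This stands in part. The absence of a confidence interval method would not be a finding by itself. But the zero-event criterion and the promise to show safety are protocol text. An analysis plan that concluded only that rates above 13.9% are excluded would not agree with them.

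A reader might infer more than the documents support, in four ways.

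- *That the plan treats a clean result as proof of safety.* The protocol does not use that word and does not say how a met milestone would be reported. It says that safety will be shown, which is enough for the point made here.
- *That the trial makes safety easier to reach by treating fewer infants.* It is true of any zero-count criterion that the chance of meeting it rises as n falls. But section 6.0 plans 20, section 1.0 also speaks of studying 20, and no interim look or early declaration is described. Smaller samples arise only on a shortfall, which the protocol neither foresees nor guards against.
- *That 0.36 is the chance of wrongly meeting the milestone.* That figure is for one event type. The full milestone needs four zeros, so at planned enrolment it may well be missed even by a tolerable device.
- *That bradycardia, as the rarest event, would probably be missed.* The protocol gives no event frequencies. At an assumed 5% rate and 20 infants, seeing at least one event is the likelier outcome (64%).

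**Conclusion.** The concern holds in this form: the stated safety conclusion is stronger than a zero count in at most 20 infants can deliver. The size is given by the bound at full enrolment, 13.9% per event type (one-sided 95%), or 16.8% as the two-sided limit, widening on any shortfall. These bounds rest only on independent infants and the chosen confidence level. The 0.36 and 0.017 figures rest in addition on an assumed 5% rate, and the second also on independence between event types. They illustrate that the all-or-nothing count misleads in both directions; they do not predict this trial's result.

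The fault does not make the trial unfit as a pilot. It affects what may be concluded from it, and it is worth correcting before results are read.

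**What to change.** In section 1.0 (Aim 1), replace the zero-count criterion with an estimate. For each of the four milestone event types, report the proportion of infants with the event among all who received any tAN, with its exact (Clopper-Pearson) one-sided 95% upper bound at the number actually treated. State the safety conclusion as the rate excluded by that bound, for example: *zero of 20 infants excludes a per-infant rate above 13.9%*. Take the list of event types from Aim 1, since section 4.0 names only two of them.

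In the Limitations paragraph of section 10.0, change the safety part of the promise to: *we will estimate event rates and their upper bounds*.

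Do not make 20 treated infants a pass/fail line. Zero of 19 gives 1 − 0.05^(1/19) = 14.6% and zero of 20 gives 13.9%, so such a threshold would be arbitrary; the bound already carries the effect of a smaller sample.

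The cost is two changes of wording and one exact bound per event type. No extra infants are needed. The downside is a more modest claim: at best, rates above about 14% excluded for each event type.
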